## 10. SAP REVISION

Revision Date (dd month, yyyy)	Section	Summary of Revision	Reason for Revision

## 11. APPENDICES

- Appendix 1. Table of Contents for Statistical Tables, Figures, and Listings
- Appendix 2. Programming Specifications

## Appendix 1. Table of Contents for Statistical Tables, Figures, and Listings

Table Number	Title	Analysis Set
1	Subject Disposition	Screened Subjects
2	Demographics and Baseline Characteristics	Safety Analysis Set
3.1	Summary of Interferon Ineligible Reason	Safety Analysis Set
3.2	Summary of Interferon Intolerant Reason	Safety Analysis Set
4	Duration of Exposure to Study Regimen	Safety Analysis Set
5	HCV Virologic Outcome	Full Analysis Set
6	SVR by Visit during Posttreatment Follow Up (SVR4 and SVR12)	Full Analysis Set
6.1	SVR by Visit during Posttreatment Follow Up (SVR4 and SVR12) by Subgroup	Full Analysis Set
7	Proportion of subjects with HCV RNA Less than LLOQ (25 IU/mL) While on Treatment by Visit	Full Analysis Set
8	Adverse Events: Brief Summary	Safety Analysis Set
9	All Treatment-Emergent Adverse Events	Safety Analysis Set
10	Treatment-Emergent Treatment-Related Adverse Events	Safety Analysis Set
11	Grade 3 or 4 Treatment-Emergent Adverse Events	Safety Analysis Set
12	Grade 3 or 4 Treatment-Emergent Treatment-Related Adverse Events	Safety Analysis Set
13	Adverse Events Leading to Permanent Discontinuation from Any of the Study Drugs	Safety Analysis Set
14	Adverse Events Leading to Permanent Discontinuation from SOF	Safety Analysis Set
15	Treatment-Emergent Serious Adverse Events	Safety Analysis Set
16	Treatment-Emergent Treatment-Related Serious Adverse Events	Safety Analysis Set
17	Treatment-Emergent Non-Serious Adverse Events Occurring in At Least 5% of Subjects in Any Treatment Group	Safety Analysis Set
18.1	ALT (U/L) and Change from Baseline by Visit	Safety Analysis Set
18.2	AST (U/L) and Change from Baseline by Visit	Safety Analysis Set
18.3	Total Bilirubin (mg/dL) and Change from Baseline by Visit	Safety Analysis Set
18.4	Alkaline Phosphatase (U/L) and Change from Baseline by Visit	Safety Analysis Set
18.5	WBC ( $\times 10^3/\mu\text{L}$ ) and Change from Baseline by Visit	Safety Analysis Set
18.6	Neutrophils ( $\times 10^3/\mu\text{L}$ ) and Change from Baseline by Visit	Safety Analysis Set
18.7	Lymphocytes ( $\times 10^3/\mu\text{L}$ ) and Change from Baseline by Visit	Safety Analysis Set

Table Number	Title	Analysis Set
18.8	Hemoglobin (g/dL) and Change from Baseline by Visit	Safety Analysis Set
18.9	Platelets ( $\times 10^3/\mu\text{L}$ ) and Change from Baseline by Visit	Safety Analysis Set
18.10	Reticulocytes ( $\times 10^3/\mu\text{L}$ ) and Change from Baseline by Visit	Safety Analysis Set
18.11	CD4 Counts ( $\text{cells}/\text{mm}^3$ ) and Change from Baseline by Visit	Safety Analysis Set
18.12	CD4 Counts (%) and Change from Baseline by Visit	Safety Analysis Set
19.1	Treatment-Emergent Graded Laboratory Abnormalities	Safety Analysis Set
19.2	Treatment-Emergent Grade 3 or 4 Laboratory Abnormalities	Safety Analysis Set
20	Shift in Toxicity Grade for Total Bilirubin from Baseline to Maximal Post-baseline Grade by Atazanavir Status at Enrollment	Safety Analysis Set
21	Proportion of Subjects with HIV Virologic Rebound for Subjects Who Were on ARV Treatment at Enrollment	Safety Analysis Set
22.1	HCV Virologic Outcome for Subjects on ARV at Baseline	Full Analysis Set
22.2	HCV Virologic Outcome for Subjects Not on ARV at Baseline	Full Analysis Set
23.1	CD4 Counts ( $\text{cells}/\text{mm}^3$ ) and Change from Baseline by Visit for Subjects on ARV at Baseline	Safety Analysis Set
23.2	CD4 Counts ( $\text{cells}/\text{mm}^3$ ) and Change from Baseline by Visit for Subjects Not on ARV at Baseline	Safety Analysis Set
23.3	CD4 Counts (%) and Change from Baseline by Visit for Subjects on ARV at Baseline	Safety Analysis Set
23.4	CD4 Counts (%) and Change from Baseline by Visit for Subjects Not on ARV at Baseline	Safety Analysis Set

Figure Number	Title	Analysis Set
1.1	Median (Q1, Q3) ALT (U/L) by Visit	Safety Analysis Set
1.2	Median (Q1, Q3) AST (U/L) by Visit	Safety Analysis Set
1.3	Median (Q1, Q3) Total Bilirubin (mg/dL) by Visit	Safety Analysis Set
1.4	Median (Q1, Q3) Alkaline Phosphatase (U/L) by Visit	Safety Analysis Set
1.5	Median (Q1, Q3) WBC ( $\times 10^3/\mu\text{L}$ ) by Visit	Safety Analysis Set
1.6	Median (Q1, Q3) Neutrophils ( $\times 10^3/\mu\text{L}$ ) by Visit	Safety Analysis Set
1.7	Median (Q1, Q3) Lymphocytes ( $\times 10^3/\mu\text{L}$ ) by Visit	Safety Analysis Set
1.8	Median (Q1, Q3) Hemoglobin (g/dL) by Visit	Safety Analysis Set
1.9	Median (Q1, Q3) Platelets ( $\times 10^3/\mu\text{L}$ ) by Visit	Safety Analysis Set
1.10	Median (Q1, Q3) Reticulocytes ( $\times 10^3/\mu\text{L}$ ) by Visit	Safety Analysis Set
1.11	Median (Q1, Q3) CD4 Counts (cells/mm  ) by Visit	Safety Analysis Set
1.12	Median (Q1, Q3) CD4 Counts (%) by Visit	Safety Analysis Set
2.1	Median (Q1, Q3) CD4 Counts (cells/mm  ) by Visit by ARV at Baseline	Safety Analysis Set
2.2	Median (Q1, Q3) CD4 Counts (%) by Visit by ARV at Baseline	Safety Analysis Set
3.1	Forest Plot of SVR4 by Subgroup	Full Analysis Swet
3.2	Forest Plot of SVR12 by Subgroup	Full Analysis Swet

Listing Number	Title	Analysis Set
1	Subject Disposition	Safety Analysis Set
2	Subject Demographics and Baseline Characteristics	Safety Analysis Set
3	Medical History	Safety Analysis Set
4	Study Drug Administration	Safety Analysis Set
5	Prior and Current HIV Medications	Safety Analysis Set
6	Subjects with HCV Virologic Failure	Full Analysis Set
7.1	HCV RNA (log10 IU/mL) and Change from Baseline for All Subjects in the FAS	Full Analysis Set
7.2	HCV RNA (log10 IU/mL) and Change from Baseline for All Subjects in the Safety Analysis Set but Not in FAS	Safety Analysis Set
8	All Adverse Events	Safety Analysis Set
9	Grade 3 or 4 Adverse Events	Safety Analysis Set

10	Adverse Events Leading to Permanent Discontinuation from Any of the Study Drugs	Safety Analysis Set
11	Adverse Events Leading to Permanent Discontinuation from SOF	Safety Analysis Set
12	Serious Adverse Events	Safety Analysis Set
13	Pregnancy	Safety Analysis Set
14	Deaths	Safety Analysis Set
15	Central Laboratory (Covance) Reference Ranges	Safety Analysis Set
16	Subjects with Treatment-Emergent Grade 3 or 4 Laboratory Abnormalities	Safety Analysis Set
17.1	Hematology: RBC, Reticulocyte Count, WBC, Lymphocytes, and Neutrophils	Safety Analysis Set
17.2	Hematology: Monocytes, Eosinophils, and Basophils	Safety Analysis Set
17.3	Hematology: Hemoglobin, Hematocrit, Platelets, and MCV	Safety Analysis Set
18	Coagulation and Thyroid Function: INR, PT, APTT	Safety Analysis Set
19.1	Chemistry: Albumin, Alkaline Phosphatase, ALT, AST, Total Bilirubin, and Direct Bilirubin	Safety Analysis Set
19.2	Chemistry: Serum Creatinine, Estimated GFR (Cockcroft-Gault)	Safety Analysis Set
19.3	Chemistry: Lipase, Potassium, Sodium, and Glucose	Safety Analysis Set
20	CD4 T-Lymphocyte Absolute Count and % and HIV RNA (copies/mL)	Safety Analysis Set
21	Height, Weight, BMI and Vital Signs	Safety Analysis Set
22.1	Subjects with HIV Virologic Rebound	Safety Analysis Set
22.2	HIV RNA, Change and Percent Change from Baseline by Visit for Subjects Not on ARV at Baseline	Safety Analysis Set

## Appendix 2. Programming Specifications

The following code will be used to calculate AGE on the DATE OF FIRST DOSE:

```
if n(brthdtn,_dtday1)=2 then do;
  age = int(intck('month', brthdtn, _dtday1)/12) ;
  if month(brthdtn)=month(_dtday1) & day(brthdtn)>day(_dtday1) then
    age=age-1 ;
  ageu = "YEARS";
end;
```

HCV Genotype will be determined from the results of LiPA 2.0 assay. If LiPa 2.0 returns a value of 'Indeterminate' or missing, then the Abbott Real time HCV Genotype 2 assay will be used. If both assays return a result of 'Indeterminate', then NS5B sequencing will determine genotype.

The following code will be used to create the 95% exact CI on the proportion:

```
data SVR12;
input resp count;
cards;
0 10
1 50
;
run;

proc freq data = SVR12 ;
weight count;
tables resp / binomial alpha=0.05;
run;
```

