## 6. EFFICACY ANALYSES

### 6.1. Definition of the Efficacy Endpoints

The efficacy endpoints for this safety update include the following:

- SVR12 defined as HCV RNA < LLOQ (ie, < 25 IU/mL) at 12 weeks after study drug cessation for the full analysis set. The Roche COBAS® Taqman® HCV Test v2.0 for use with the High Pure System will be used to measure HCV RNA.
- Sustained virologic response 4 weeks after stopping all study drugs (SVR4) defined as HCV RNA < LLOQ (ie, < 25 IU/mL) at 4 weeks after study drug cessation for the full analysis set
- The proportion of subjects with HCV RNA below LLOQ (ie, < 25 IU/mL) while on treatment by study visit
- The proportion of subjects with on-treatment and posttreatment virologic failure, defined as the following:
  - On-treatment virologic failures
    - HCV RNA  $\geq$  25 IU/mL after having previously had HCV RNA < 25 IU/mL while on treatment, confirmed with 2 consecutive values (Note: second confirmation value can be posttreatment) or last available on-treatment measurement with no subsequent follow-up values (ie, breakthrough)
    - $>1 \log_{10}$  IU/mL increase in HCV RNA from nadir while on treatment, confirmed with 2 consecutive values (Note: second confirmation value can be posttreatment) or last available on-treatment measurement with no subsequent follow up values (ie, rebound)
    - HCV RNA persistently  $\geq$  25 IU/mL through 8 weeks of treatment (ie, nonresponse)
  - Relapse
    - HCV RNA  $\geq$  25 IU/mL during the posttreatment period having achieved HCV RNA < 25 IU/mL at end of treatment, confirmed with 2 consecutive values or last available posttreatment measurement

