### 6.2. Analysis of the Efficacy Endpoint

The efficacy endpoints will be derived for all subjects in safety analysis set using observed HCV RNA data and imputation rule specified in section 3.6.

For analyses of HCV RNA < LLOQ (ie, < 25 IU/mL) by visit while on treatment, subjects will be assigned a value at each visit based on the categorical imputation rules described in Section **Error! Reference source not found.** The 2-sided 95% exact confidence interval (CI) based on Clopper-Pearson method will be provided for the proportion {20839}. The overall category for “HCV RNA < LLOQ” will be split into the following 2 subcategories: “< LLOQ TND” for subjects with target not detected and “< LLOQ detected” for subjects with < LLOQ in tabular displays.

The point estimate of SVR4 and SVR12 rate and 2-sided 95% exact confidence interval (CI) will be provided for each treatment group and for each treatment group within each subgroup specified in section 3.4. A Forest plot will graphically present estimates and 95% confidence intervals of SVR4 and SVR12 rates for each treatment group within each subgroup.

For the SVR12 endpoint analysis, a summary table of the number and percentage of subjects with SVR12, virologic failure, and other will be created. All subjects who achieve SVR12 will be categorized as SVR12. Virologic failure will be descriptively summarized as “on-treatment virologic failure” and relapse (which will be summarized by study drug completed yes or no). Subjects who do not achieve SVR12 and do not meet criteria for virologic failure will be categorized as other. The denominator for relapse will be the number of subjects who had HCV RNA < LLOQ on their last observed on-treatment HCV RNA measurement; otherwise, the denominator will be the number of subjects in the FAS.

Details regarding SAS programming are provided in the programming specifications in **Error! Reference source not found.** of this SAP.

A data listing of HCV genotype, cirrhosis, IL28B, scheduled visit, analysis visit window, date of HCV RNA sample collection, HCV RNA load (categorical and numeric), and change from baseline for on-treatment visits will be provided for the following:

- 1), subjects with HCV virologic failure in the FAS;
- 2), all subjects in the FAS
- 3), all subjects in the safety analysis set but not in FAS

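### The SAS code prescribed in SAP Appendix 2 for the exact 95% CI targets the non-responder level and switches target in cells where every subject responds

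*Combined protocol and SAP*

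**What the plan says.** SAP Section 6.1 sets the target as response: "SVR12 defined as HCV RNA < LLOQ (ie, < 25 IU/mL) at 12 weeks after study drug cessation for the full analysis set". Section 6.2 asks for exact intervals in two places. For on-treatment suppression by visit: "The 2-sided 95% exact confidence interval (CI) based on Clopper-Pearson method will be provided for the proportion". For the SVR endpoints: "The point estimate of SVR4 and SVR12 rate and 2-sided 95% exact confidence interval (CI) will be provided for each treatment group", repeated within every subgroup of Section 3.4 and shown in forest plots.

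Section 6.2 then refers to the programming specifications. The cross-reference is broken, but Appendix 2 carries that title. Its lead-in reads: "The following code will be used to create the 95% exact CI on the proportion". The code builds a data set named SVR12 with "input resp count", enters resp=0 with a count of 10 and then resp=1 with a count of 50, and calls "proc freq data = SVR12" with a WEIGHT statement on count and "tables resp / binomial alpha=0.05".

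The code contains no LEVEL=, ORDER= or ZEROS. Nothing in the SAP says what resp=1 means, directs the calculation to that level, or asks for a complement to be taken.

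**The concern.** The SAP wants the interval for the proportion who respond. With 0/1 data and no level requested, the procedure has to choose one, and by default it takes the first in ascending order, which is 0. If 0 is a non-responder, the interval describes failures.

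A constant inversion would be easy to undo, because exact limits for a proportion and for its complement mirror each other. This inversion is not constant. When a cell has no non-responders, the first remaining level is 1 and the code silently reports responders. A blanket one-minus correction would then turn a 100% cell into 0%.

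At stake are the intervals for SVR4, SVR12 and on-treatment suppression by visit, including intervals that a program would extract cell by cell for the forest plots, where mixed targets are harder to see.

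**Working it through.** **Inputs.** From Appendix 2: resp=0 count 10, resp=1 count 50, so n = 60, alpha 0.05. From Section 6.2: two-sided exact limits, with Clopper-Pearson named for the by-visit proportions.

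**Assumptions.** (a) resp=1 means responder. (b) PROC FREQ defaults: levels in ascending order, BINOMIAL reports the first level, zero-weight rows are dropped unless ZEROS is given. SAS was not run; the limits below are beta quantiles for the level these defaults select.

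**The plan's own interval figures.** Appendix 2 prints no output for its example. The only interval figures in the SAP are the half-widths in Section 1.3, which follow from 1.96 × √(p(1−p)/n):
- n = 55, p = 0.62: 12.83% (stated 12.8%)
- n = 55, p = 0.40: 12.95% (12.947% unrounded; stated 12.9%)
- n = 115, p = 0.65: 8.72% (stated 8.7%)

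They reproduce from the normal approximation and do not depend on the code.

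**Formula.** For x of n, the lower limit is the 0.025 quantile of Beta(x, n−x+1) and the upper limit is the 0.975 quantile of Beta(x+1, n−x). For x = n, the lower limit is 0.025^(1/n) and the upper limit is 1.

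| Responders/n | Level reported | As coded | Intended |
|---|---|---|---|
| 50/60 (SAP example) | 0 | 16.7% (8.3 to 28.5) | 83.3% (71.5 to 91.7) |
| 59/60 | 0 | 1.7% (0.04 to 8.9) | 98.3% (91.1 to 99.96) |
| 60/60 | 1 | 100% (94.0 to 100) | 100% (94.0 to 100) |
| 0/60 | 0 | 100% (94.0 to 100) | 0% (0 to 6.0) |
| 9/10 | 0 | 10.0% (0.3 to 44.5) | 90.0% (55.5 to 99.7) |
| 10/10 | 1 | 100% (69.2 to 100) | 100% (69.2 to 100) |
| 22/55 (planned 40%) | 0 | 60.0% (45.9 to 73.0) | 40.0% (27.0 to 54.1) |

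One extra responder moves the printed value from 1.7% to 100%, and total success and total failure print the same numbers. ORDER=DATA would not help, since 0 is entered first. ORDER=FREQ would put 1 first in the SAP example, but it is not specified.

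**How likely are all-responder cells?**
- *On treatment.* Protocol Table 1-5 shows 100% of subjects below the limit of detection at Week 4 and at end of treatment in every column. Table 1-7 shows 19/19 and 6/6 below LLOQ at Week 4 in both duration groups. As an illustration, the genotype 1 treatment-naive column of Table 1-5 has 17/25, 22/25 and 25/25 at Weeks 2, 3 and 4. The code would print 8/25 = 32%, 3/25 = 12% and then 100%, instead of 68%, 88% and 100%.
- *SVR subgroups.* At the planned 62%, the chance that all n respond is 0.62^n: 24% for n = 3, 9% for n = 5, 0.8% for n = 10.

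**The case against.** The strongest reply is that the snippet is a template. It carries dummy counts that match no planned group, a programmer must adapt it, and the body of the SAP fixes the target and the method correctly. That limits the damage but does not remove the defect: the lead-in says this code will be used, and no text tells the programmer to change the level.

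A second reply is that the meaning of resp and the PROC FREQ default are not stated in the documents. That is fair for the coding. If 0 meant responder, mixed cells would come out right. The switch would remain, though: a cell with no responders would then report 100% for the other level. The default is standard documented behaviour of the software that the SAP names, but it is stated here as an assumption because SAS was not run.

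A third reply is that the error would be seen. Section 6.2 separately tabulates the number and percentage with SVR12, and an interval of 8.3 to 28.5 beside 83.3% is an obvious mismatch. This stands for the main results. It weakens as rates approach 50%, where the two intervals coincide.

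A reader might also infer that all-responder SVR cells will be common across the subgroups. The planned rates of 62%, 40% and 65% do not support that beyond very small cells.

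**Conclusion.** The code is wrong as written, under two assumptions: resp=1 is the responder, and PROC FREQ reports the first displayed level. On the SAP's example it gives 16.7% (8.3 to 28.5) where 83.3% (71.5 to 91.7) is intended, and in all-responder cells it changes target. All-responder cells are plausible mainly for on-treatment suppression by visit and for very small SVR subgroups.

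Two stronger readings are tempting. One is that the primary SVR12 percentage itself is mis-specified. Appendix 2 prescribes the code only for the interval, and the SVR12 counts and percentages are tabulated separately. The other is that wrong results were reported, and nothing in the documents shows that. The design, endpoint definition, interval method and sample-size figures are untouched. This is an error in the programming specification that should be corrected, not a flaw in the analysis strategy.

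**What to change.** In Appendix 2:
1. State that resp=1 is a responder (HCV RNA below LLOQ) and resp=0 is not.
2. Request the responder level explicitly, for example `tables resp / binomial(level='1') alpha=0.05;`, after confirming the syntax in SAS 9.1, the version named in SAP Section 9. Alternatively, code the variable so that success always sorts first.
3. For 0% and 100% cells, supply both levels with `weight count / zeros;`, or compute the limits directly from beta quantiles.
4. Validate against 50/60 = 83.3% (71.5 to 91.7), an all-success cell (60/60: 94.0 to 100) and an all-failure cell (0/60: 0 to 6.0).

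The cost is one line of code and a short validation check. No data, endpoint or sample-size change is needed.
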